6.3.1 Medical history - Core phase

Medical history and ongoing conditions will be summarized and listed for all patients. Separate summaries will be presented for ongoing and historical medical conditions. The summaries will be presented by primary system organ class and preferred term. Medical history/current medical conditions are coded using the Medical Dictionary for Regulatory Activities (MedDRA) terminology using the latest version available (Version. 22.0) prior to clinical database lock.

6.4 Treatments (study drug, other concomitant therapies)

6.4.1 Extent of exposure of cabergoline

All study medication data will be summarized using the safety set.

6.4.1.1 Dose intensity and exposure - Core and extension phase

Duration of exposure will be summarized by appropriate descriptive statistics. The following definitions will be used:

Treatment start date: defined as the first date at which a non-zero dose of cabergoline is administered during the study and recorded on the Dosage Administration Record (DAR) eCRF over core and extension phase for safety set.

6.4.1.1.1 Core and extension phase

Treatment end date (extension phase): defined as the last date at which a non-zero dose of cabergoline was administered and recorded on the DAR eCRF for patients who discontinue before the final cutoff date of the extension phase or who complete the extension phase with the final cutoff date recorded on the VIS eCRF.

Duration of exposure (core and extension phase): will be calculated as the number of days from the treatment start date to the treatment end date above, including days with interruptions.

duration of exposure for extension phase = treatment end date (final cutoff date) – treatment start date + 1.

6.4.1.1.2 Dose exposure and intensity

Dose intensity of cabergoline will be calculated for each patient as total cumulative dose at the time of last administration divided by the duration of exposure.

Duration of exposure and dose intensity while in the study will be summarized with descriptive statistics over the core phase. A frequency table will show the number and percentage of patients per duration of exposure category: core phase category (≤ 8 weeks, >8 to 17 weeks, >17 to 35 weeks, >35 to 40 weeks). For core and extension phase: (≤ 8 weeks, >8 to 17 weeks, 17-35 weeks, >35 to 43 weeks, >43 to 98 weeks, >98 to 153 weeks, >153 to 208 weeks, >208 to 263 (up to final week)).

6.4.2 Extent of exposure of pasireotide s.c. alone or in combination with cabergoline

6.4.2.1 Dose intensity and exposure - Core and extension phase

All study medication data will be summarized using the safety set.

Duration of exposure will be summarized by appropriate descriptive statistics. The following definitions will be used:

Treatment start date: defined as the first date at which a non -zero dose of pasireotide s.c. alone or in combination with cabergoline, administered during the study and recorded on the Dosage Administration Record (DAR) eCRF.

Treatment end date (extension phase): defined as the last date at which a non-zero dose of pasireotide was administered and recorded on the DAR eCRF for patients who discontinued before the last cutoff date of the extension phase or who complete the extension phase with the final cutoff date recorded on the VIS eCRF.

Duration of exposure (core and extension phase): will be calculated as the number of days from the treatment start date to the treatment end date above, including days with interruptions.

duration of exposure = treatment end date (extension phase) – treatment start date + 1

6.4.2.1.1 Dose exposure and intensity

Dose intensity of pasireotide s.c. alone or in combination with cabergoline will be calculated for each patient as total cumulative dose at the time of last administration divided by the duration of exposure.

Duration of exposure and dose intensity while in the study will be summarized with descriptive statistics over the core phase. A frequency table will show the number and percentage of patients per duration of exposure category: core phase category (≤ 8 weeks, >8 to 17 weeks, >17 to 35 weeks, >35 to 40 weeks). For core and

extension phase:(≤ 8 weeks, >8 to 17 weeks, 17-35 weeks, >35 to 43 weeks, >43 to 98 weeks, >98 to 153 weeks, >153 to 208 weeks, >208 to 263 (up to final weeks)).

6.5 Efficacy evaluation

6.5.1 Primary efficacy evaluation for core and extension phase

The primary efficacy endpoints are:

- Proportion with corresponding asymptotic 95% CI of patients who attain mean of urinary free cortisol (mUFC) $\leq 1.0 \times \text{ULN}$ at date-cutoff date with pasireotide alone or in combination with cabergoline for FAS and Extension FAS set.

Handling of missing value/censoring/discontinuation is described in [Section 8.3.2](#).

A responder is a patient who has $\text{mUFC} \leq \text{ULN}$.

Last observation carried forward (LOCF) methodology will be used for mUFC assessment for the core phase. The primary efficacy at end of core phase date (week 35) and cut-off of the extension phase will be summarized by baseline mUFC categories. The primary efficacy endpoint will be summarized within each of the three mUFC levels at baseline:

- $1 \times \text{ULN} < \text{baseline mUFC} \leq 2.0 \times \text{ULN}$
- $2 \times \text{ULN} < \text{baseline mUFC} \leq 5.0 \times \text{ULN}$
- $\text{baseline mUFC} > 5.0 \times \text{ULN}$

These analyses will be performed on FAS and EXTENSION FAS.

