#### **6.7.1 Prohibited concomitant therapy**

PRAR $\gamma$  agonists (rosiglitazone or pioglitazone) treatment is not permitted during the study as it could affect patient's ACTH levels. Treatment with prednisolone is prohibited as this interferes with the UFC detection. Use of the medications listed in below that requires a washout are also prohibited during the study.

Further, the use of concomitant medications with a known risk for QT prolongation is prohibited and requires the discontinuation of the patient from the study prior to starting the respective QT prolonging medication. Please refer to [Appendix 4](#) for guidance regarding medications which pose a known risk for QT prolongation.

Patients on medical treatment for Cushing's disease the following washout periods must be completed before screening assessments are performed:

1. Inhibitors of steroidogenesis (ketoconazole, metyrapone): 1 week
2. Pituitary directed agents: Dopamine agonists (bromocriptine, cabergoline) and PPAR $\gamma$  agonists (rosiglitazone or pioglitazone): 4 weeks
3. Octreotide LAR, Lanreotide SR and Lanreotide autogel: 14 weeks
4. Octreotide (immediate release formulation): 1 week
5. Progesterone receptor antagonist (mifepristone): 4 weeks
6. Pasireotide s.c.: 2 weeks
7. Pasireotide LAR: 12 weeks

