#### **10.2.2.1 Statistical hypothesis, model, and method of analysis**

The trial is exploratory in nature and no formal hypothesis testing is planned.

- The proportion of patients with normalized mUFC at week 35 will be reported along with its corresponding asymptotic 95% CI.

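### The responder rule does not cover an mUFC measured while the patient takes another, prohibited Cushing's drug, so such a patient can count as a success of the study regimen

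*SAP*

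**What the plan says.** **Response.** SAP 6.5.1 states: "A responder is a patient who has" mUFC at or below ULN. It applies this at week 35 and at the extension cut-off, and adds: "These analyses will be performed on FAS and EXTENSION FAS". Protocol 10.2.2.1 gives the primary analysis: "The proportion of patients with normalized mUFC at week 35 will be reported along with its corresponding asymptotic 95% CI".

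**Non-response.** Protocol 10.2.3 carries forward an assessment from week 31 or later when week 35 is missing, and makes patients who discontinue before week 35 non-responders. It names no other event. SAP 6.5.1 says "Handling of missing value/censoring/discontinuation is described in" Section 8.3.2. The available SAP text ends at 6.6.6, so that section cannot be read.

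**Prohibited drugs.** Protocol 6.7.1 gives a list of Cushing's treatments with washout periods, for example "Inhibitors of steroidogenesis (ketoconazole, metyrapone): 1 week", and says: "Use of the medications listed in below that requires a washout are also prohibited during the study". The list also covers dopamine agonists, PPAR-gamma agonists, octreotide and lanreotide, mifepristone and pasireotide itself. For PPAR-gamma agonists 6.7.1 adds that "treatment is not permitted during the study as it could affect patient's ACTH levels". Only QT-prolonging drugs carry a stated consequence, which is discontinuation (6.7.1 and 7.1.2.1).

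**Per-protocol set.** Protocol 10.2.4 plans a supportive analysis of the primary endpoint in patients without major violations. SAP 5.3 keeps this set but places the deviation criteria in other documents. SAP 6.5.1 does not name the set.

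**The concern.** The primary endpoint is meant to show what the study regimen achieves. Protocol 6.7.1 treats other Cushing's therapies as incompatible with that aim, but the responder rule does not ask whether one was being taken when the urine was collected.

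The patients most likely to be given another drug are those whom the regimen has not controlled. If the added drug brings mUFC down to normal, a patient who would have been a failure is counted as a success. There is no control arm in which the same thing could happen and cancel out.

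The scenario is not far-fetched. The title in protocol section 13 of the stepwise study used as rationale in 2.1 names ketoconazole as a further drug with pasireotide and cabergoline, and ketoconazole is on the 6.7.1 list.

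**Working it through.** **1. The passages side by side.** Take a patient who starts metyrapone in week 28, stays on study drug and has a normal mUFC at week 35.

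- Protocol 6.7.1: the use is prohibited, but no discontinuation is stated.
- Protocol 7.1.2.1: withdrawal for lack of efficacy needs UFC to stay raised without clinical benefit. If the added drug normalises UFC, that criterion is not met.
- Protocol 10.2.3: the patient has not discontinued and the week-35 value is present, so nothing makes the patient a non-responder.
- SAP 6.5.1: mUFC is at or below ULN, so the patient is a responder in the FAS.

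**2. The plan's own figure.** Protocol 10.5 assumes 34% response, N = 64, 10% drop-out and a precision of 12.8%.

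- Weighted rate: (58 × 35% + 6 × 28%)/64 = 34.3%.
- Evaluable patients: 64 × 0.9 = 57.6, about 58.
- The half-width of an exact (Clopper-Pearson) 95% interval at 34% with n = 58 is 12.8%, so the figure reproduces.
- The asymptotic interval planned for the analysis gives 1.96 × √(0.34 × 0.66/57.6) = 12.2%.

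This figure does not depend on the point at issue. It serves as a yardstick.

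**3. Effect per patient.** One reclassified responder moves the rate by 1/64 = 1.6 points, and three move it by 3/64 = 4.7 points. Against the stated precision, 4.7/12.8 = 0.37. The table assumes 22 observed responders among 64, of whom k had mUFC collected on a prohibited Cushing's drug. The documents give no value for k.

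| k | Responders | Rate | Asymptotic 95% CI |
|---|---|---|---|
| 0 | 22/64 | 34.4% | 22.7 to 46.0 |
| 1 | 21/64 | 32.8% | 21.3 to 44.3 |
| 3 | 19/64 | 29.7% | 18.5 to 40.9 |
| 6 | 16/64 | 25.0% | 14.4 to 35.6 |

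The Extension FAS is a subset of the FAS and its size is not given. Each patient weighs at least as much there.

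**4. Exclusion is not the same as failure.** With k = 3, counting non-response gives 19/64 = 29.7%. Excluding the three, as a per-protocol analysis would if nobody else were excluded, gives 19/61 = 31.1%.

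**The case against.** **The rule may exist elsewhere.** SAP Section 8.3.2, the core-phase SAP and the deviation criteria are not in the available text. This stands, and the point is conditional on it. Protocol 10.2.3, which covers the same topic, has no such rule.

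**Safeguards exist.** The drugs are prohibited, so taking one is a deviation, and protocol violation is among the reasons for which a patient may be withdrawn. Uncontrolled patients are titrated upwards, must be withdrawn if the regimen keeps failing, and are non-responders if they discontinue. Appendix 4 only links to an external list of QT-prolonging drugs, so the documents do not show whether any Cushing's drug also falls under that discontinuation rule. All this narrows the route to patients who stay on study drug while taking a prohibited one, but does not close it. The per-protocol analysis helps only if such use is classed as a major violation. It removes the patient instead of counting a failure, and the final SAP does not list it for the primary endpoint.

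**The size is hypothetical.** This also stands. The trial is exploratory with no hypothesis test, and three patients would shift the rate by less than its planned precision.

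**Stronger readings that the documents do not support.**

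- A reader might infer that every listed drug is barred because it alters cortisol. Protocol 6.7.1 does not say so: it gives an ACTH reason for PPAR-gamma agonists and an assay reason for prednisolone, and describes the washout list only as medical treatment for Cushing's disease. Protocol 1.2.1 calls the studies of octreotide and lanreotide in this disease unsuccessful.
- From "Treatment with prednisolone is prohibited as this interferes with the UFC detection" a reader might infer that the rule wrongly omits other glucocorticoids. The documents describe neither the assay nor any other interfering drug, so this has no basis in them. Setting such values to missing could also bring a week-31 response forward.

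**Conclusion.** The point holds as a gap in the endpoint definition. Under the text available, a normal mUFC obtained with the help of a prohibited Cushing's drug counts as a success of the regimen, provided the patient remains on study drug.

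The size is 1.6 points per such patient at week 35. That is the full bias only if the patient would have been above ULN without the added drug; a patient who would have responded anyway adds none. The total is unknown because the number of users is not given.

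The documents do not support the inference that the reported rate is in fact inflated, or that such use became more common in the extension. The conclusion assumes that no rule exists in SAP Section 8.3.2 or the core-phase SAP.

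**What to change.** State in SAP 6.5.1 and protocol 10.2.3:

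- An mUFC collected while the patient is taking a non-study Cushing's medication from the 6.7.1 list, or within the 6.7.1 washout period for that drug, counts as non-response in the primary and by-visit response analyses. Cabergoline and pasireotide given as study treatment are outside the rule, although both names are on the list.
- For duration of response, the start of such a drug ends the response.
- Use is identified from the concomitant-medication CRF, and the number of users is reported.

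The washout periods were set for screening. Using them here is a choice, and the SAP should say so. If Section 8.3.2 or the core-phase SAP already has an equivalent rule, a citation in 6.5.1 is enough.

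The SAP is an addendum issued after database lock. Label the change as post-lock and report the rate under the present 6.5.1 definition beside the new one.

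The cost is a few sentences and a merge with medication data that protocol 6.7 already requires. Reclassification can only lower the response rate or leave it unchanged, so the result may be slightly less favourable.

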6.5.2 Secondary efficacy evaluation

The secondary efficacy endpoints will be summarized for the FAS and EXTENSION FAS for parameters from baseline measurements over core phase to week 35 and extension phase from week 43 to final cutoff date at each scheduled assessment:

1. Actual and percentage change in mUFC from baseline to each scheduled visit when UFC is measured until the final cut-off date
2. Proportion of patients with normalized mUFC (i.e $\text{mUFC} \leq 1.0 \times \text{ULN}$) as assessed at each scheduled visit when UFC is measured until the final cut-off date
3. Proportion of patients, at each visit, who attained $\text{mUFC} \leq 1.0 \times \text{ULN}$ (controlled) or have at least 50% reduction (partially controlled) from baseline in mUFC as assessed at

each scheduled visit when UFC is measured until the final cut-off date

4. Duration of controlled or partially controlled response is defined as the period starting from the date of patient's first normalization ($mUFC \leq 1.0 \times ULN$) or at least 50% reduction from baseline up to the date when the patient's $mUFC > 1.0 \times ULN$ and the reduction from baseline falls to less than 50% from the first time until the final cut-off date

5. Actual and percentage changes from baseline, at each scheduled post baseline visit, in plasma ACTH and serum cortisol over visit time window until the final cut-off date

6. Actual and percentage change from baseline over visit time window in clinical symptoms of Cushing's disease: blood pressure, body mass index, waist circumference, fasting serum lipid profile, and weight until the final cut-off date

7. Change from baseline in clinical signs of Cushing's disease: facial until the final cut-off date

8. Rubor, supraventricular and dorsal fat pads, hirsutism, striae (via photographs) and muscle strength until the cut-off date

9. Change from baseline in standardized scores, as measured by the Cushing's QOL and SF-12v2 over time until the final cut-off date

10. Toxicity assessed by using the National Cancer Institute-Common Toxicology Criteria Adverse Events version 4.0 (NCI-CTCAE v.4) and for laboratory assessments (biochemistry, hematology, urinalysis); special safety assessments (regular monitoring and recording of blood glucose, insulin, HbA1c, GH and IGF-1, thyroid and liver function tests, gallbladder examinations and ECGs). Concomitant medications/Significant non-drug therapies will be assessed from study enrollment until the final safety date cutoff visit.

Assess the changes in mUFC from baseline to study end at each scheduled visit where UFC is measured – Core and extension phase

Descriptive summaries of actual and percentage change in mean 24h-UFC from baseline to each scheduled visit where UFC is measured will be provided along with corresponding two-sided 95% CIs.

Assess overall efficacy of pasireotide alone or in combination with cabergoline as measured by controlled and partially controlled mUFC levels at each scheduled visit until the final cut-off date

Proportion patients with normalized mUFC (i.e. $mUFC \leq 1.0 \times ULN$) at each scheduled visit will be reported along with its corresponding 95% CI until the final cut-off date

Proportion of patients who attained $mUFC \leq 1.0 \times ULN$ (controlled) or have at least 50% reduction (partially controlled) at each scheduled visit will be reported along with its corresponding 95% CI. If mUFC is missing, no imputation will be done.

Evaluate the duration of controlled or partially controlled mUFC response – Core and extension phase

Duration of controlled or partially controlled response is defined as the period starting from the date of patient's first normalization ($mUFC \leq 1.0 \times ULN$) or at least 50% reduction from baseline up to the date when the patient's $mUFC > 1.0 \times ULN$ and the reduction from baseline falls to less than 50% for the first time. Patients without a loss of response will be censored at their last available mean UFC assessment date (during the core phase). The median and 95% confidence interval of duration of response will be derived from Kaplan-Meier method.

Assess the effect on plasma ACTH and serum cortisol - Core and extension phase

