## **Amendment 4 (12-Jul-2017)**

The main objectives of this protocol amendment are as follows:

- Participating patients currently have the option to continue study treatment if pasireotide is not yet approved for commercial use and/or reimbursed - if country reimbursement is applicable - in each respective country, or until 31st December 2017, whichever occurs first. At the time of this protocol amendment, pasireotide is not yet approved for commercial use and/or reimbursed in several participating countries. In order to continue to provide access to treatment for patients in these countries and to collect longer-term safety and efficacy data, the maximum duration of the extension phase of the study will be extended by two further years, to 31st December 2019. The first results from the interim analysis related to the core phase have become available and support the use of the combination treatment, justifying the continued use of study medication.

All current procedures and collections will still be done.

[figure not shown]
The main changes to the protocol and the sections affected are detailed below:

- List of Abbreviations section: Multiple abbreviations were updated
- Section 4.1, Extension Phase Section was updated to extend the trial until 31Dec2019
- Section 6.2.2, Extension Phase Section was updated to extend the trial until 31Dec2019
- Section 8.2.2, Reporting section was updated to replace Drug Safety & Epidemiology (DS&E) with Chief Medical Office & Patient Safety (CMO&PS)
- Section 8.4, Pregnancy section was updated to replace Drug Safety & Epidemiology (DS&E) with Chief Medical Office & Patient Safety (CMO&PS)
- Multiple grammatical errors corrected throughout

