**Evaluate the duration of controlled or partially controlled mUFC response.**

Duration of controlled or partially controlled response is defined as the period starting from the date of patient's first normalization (mUFC  $\leq$  1.0xULN) or at least 50% reduction from baseline up to the date when the patient's mUFC  $>$  1.0xULN and the reduction from baseline falls to less than 50% for the first time. Patients without a loss of response will be censored at their last available mean UFC assessment date. The median and 95% confidence interval (CI) of duration of response will be derived from Kaplan-Meier curve and will be presented.

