5.1 Full analysis set

The Full Analysis Set (FAS): comprises all patients to whom study treatment has been assigned at core phase, including all group 1 and group 2 subjects. FAS will be used in analysis for the core phase.

Extension Full analysis set (Extension FAS): a subset of FAS, included patients to whom study treatment has been assigned in extension phase, including all group 1 and group 2 subjects.

Extension FAS will be used to summarized data from week 43 to final cutoff week data, unless it is specified, EXTENSION FAS and will be used to combine the core and extension phase data for some analyses.

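### SAP 6.5.2 censors continuing responders at their last core-phase mUFC in a core-plus-extension analysis, contrary to protocol 10.3; if extension losses count as events, the curve beyond about 31 weeks is biased downward

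*SAP*

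**What the plan says.** In SAP 6.5.2 the analysis is headed "Evaluate the duration of controlled or partially controlled mUFC response – Core and extension phase". Item 4 of the endpoint list in the same section ends a response when mUFC is above the ULN and "the reduction from baseline falls to less than 50% from the first time until the final cut-off date". SAP sections 1 and 4 describe a combined final analysis of both phases, cut at 30 June 2019.

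The method paragraph under that heading then gives the censoring rule: "Patients without a loss of response will be censored at their last available mean UFC assessment date (during the core phase", where the parenthesis closes. Protocol 10.3 has "Patients without a loss of response will be censored at their last available mean UFC assessment date" and stops there. Both documents ask for a Kaplan-Meier median with a 95% CI. The SAP's document history records no change to this rule and no reason for the added limit.

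On analysis sets, SAP 5.1 assigns the FAS to the core phase and adds "EXTENSION FAS and will be used to combine the core and extension phase data for some analyses", without saying which analyses. For the primary endpoint, SAP 6.5.1 states "Handling of missing value/censoring/discontinuation is described in" Section 8.3.2. That section is not in the supplied text and could not be checked.

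**The concern.** Kaplan-Meier estimation needs censoring that carries no information about the later outcome. Here a patient who loses response in the extension would be followed to the date of loss, while a patient who keeps responding for years would have follow-up ended in the core phase. Time at risk then depends on failing.

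Duration of response is a stated secondary objective, and Amendment 4 extended the study partly "to collect longer-term safety and efficacy data". The affected part of the curve is the part that only the extension can inform. A reader could take an artificial fall after the core phase for poor durability.

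The consequence depends on how the paragraph is read:

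- **Reading A (literal).** Losses count whenever they occur up to cut-off; patients without a loss are censored in the core phase.
- **Reading B.** Losses are also cut at week 35.
- **Reading C.** The parenthesis was meant only for a core-phase run on the FAS, with a separate Extension FAS run to cut-off.

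**Working it through.** The plan gives no median, event count or other figure for this endpoint, so there is nothing to reproduce. The check uses the visit schedule.

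**Inputs.** Core mUFC visits at weeks 4, 8, 13, 17, 22, 26, 31 and 35, then week 43 and every 8 weeks (protocol 7.2.1.1). Follow-up reaches about 263 weeks (top exposure category, SAP 6.4.1.1.2).

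**Step 1: longest censored time under reading A.** For a response starting at week *s*, core censoring falls no later than 35 − *s*. The maximum is 35 − 4 = 31 weeks.

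**Step 2: earliest extension loss.** This is 43 − *s*: 39 weeks for *s* = 4, and 8 weeks for *s* = 35.

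**Step 3: risk set beyond 31 weeks.** Patients without a loss, and patients with a core loss, all have times of at most 31 weeks. Only extension losses exceed it. With S(t) = ∏(1 − dᵢ/nᵢ), everyone at risk beyond 31 weeks is a later event, so at the last loss n = d and S = 0, whatever the true durability.

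**Step 4: worked example.** Suppose 20 responders enter the extension with no core losses. Five lose response one at a time after 31 weeks, and 15 are still responding beyond the last loss.

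- Protocol rule: (19/20)(18/19)(17/18)(16/17)(15/16) = 15/20 = 0.75; median not reached.
- Reading A: the risk set is 5 and the curve steps through 4/5 = 0.8, 0.6, 0.4, 0.2, 0; the reported median is the third loss.

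**Step 5: size over a range.** Assumptions not in the documents: exponential durations, 25 or 50 responders, 30% or 50% entering the extension, extension follow-up uniform from week 43 to 263, and onset early or uniform over weeks 4–31. There were 400 runs in each of 48 scenarios on the protocol's visit grid. Kaplan-Meier median in weeks:

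| True median | Protocol rule | Reading A |
|---|---|---|
| 20 | 22–23 | 22 |
| 30 | 31–33 | 30–31 |
| 40 | 42–46 | 37–39 |
| 60 | 61–63 | 47–55 |
| 100 | 99–106 | 59–64 |
| 150 | 143–164 | 68–78 |

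With a true median of 100 weeks, the true proportion still in response at 104 weeks is 2^(−104/100) = 0.49. The protocol rule estimates 0.48–0.50 and reading A 0.23–0.27.

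A second set of scenarios had 40,000 responders each, 45% or 100% entering the extension, and onset at week 4, mostly early, or spread over weeks 4–35. For a true median of 52 weeks the estimate falls from 55 to 47; for 104 weeks, from 103–111 to 66–71.

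**Step 6: reading B.** No such bias arises, but the curve stops at 31 weeks. In the 48 scenarios the median was not reached in 2–18% of runs at a true median of 20 weeks, 39–52% at 30, 69–88% at 40, 87–100% at 60 and 97–100% at 100.

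**The case against.** The strongest reply is that only reading A produces bias and the censoring sentence does not say how extension losses are treated. The final cut-off wording in item 4 is attached to almost every secondary endpoint in the list, so it is weak evidence of a deliberately wider event window. Reading C has real support: SAP 5.1 gives the FAS to the core phase, the lead-in to SAP 6.5.2 names both sets, and SAP section 1 points to an earlier core-phase plan from which the parenthesis may have been carried over. That plan was not supplied. This part stands: the conflict in wording is certain, the bias is conditional. But the duration paragraph describes no pair of runs, so the text needs correcting under every reading.

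The 31-week mark is also less sharp than it sounds. It is where the risk set becomes events only. For responses starting after week 4, a small bias can begin earlier; in the second set of scenarios it reached about 3.5 percentage points at week 31 (0.826 against 0.791). The exposure category in SAP 6.4.1.1.2, ">17 to 35 weeks, >35 to 40 weeks", might suggest a later boundary of 40 − 4 = 36 weeks, but it classifies exposure, and the last scheduled core mUFC is at week 35.

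Finally, the endpoint is descriptive, protocol 10.2.2.1 plans no hypothesis test, and nothing in the documents shows that the median lies where the shift matters. All of this is right, and it limits the weight of the point.

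**Conclusion.** The concern holds. As written, the censoring rule contradicts the SAP's own heading, its item 4 and protocol 10.3.

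If extension losses count as events, the direction of the bias and the events-only risk set beyond 31 weeks follow from the visit schedule and need no distributional assumption. The size does: the median is essentially unchanged at true medians of 20–30 weeks and about 35–45 weeks too low at 100 (59–64 against 99–106), given exponential loss and the assumed extension entry. If events are also cut at week 35, the harm is discarded extension data and a median that often cannot be estimated. If two separate runs were intended, there is no harm beyond the missing statement.

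The core-phase limit has a further gap: a patient who first responds in the extension and keeps responding would be censored before the response began. Patients who never enter the extension are handled correctly under either rule. The primary result is not affected.

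**What to change.** Delete the four-word parenthesis from the censoring sentence in SAP 6.5.2, so that patients without a loss are censored at their last available mUFC in either phase, up to the final cut-off. This restores the protocol 10.3 rule and also covers responses that begin in the extension.

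If a core-only estimate is wanted as well, define it as a separate FAS analysis with both events and censoring cut at week 35, and label it so.

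The cost is one changed sentence and one rerun Kaplan-Meier analysis. Because the current SAP is already an addendum dated after database lock, the correction should be documented as a post-lock change that restores the protocol rule. There is precedent: the October 2019 addendum added the Karnofsky analysis, which the protocol contained and the SAP had left out.
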